The effect of progressive balance exercise on postural sway – a 4 week randomized controlled trial

Today most fracture prevention measures targets the bone and osteoporosis. However, only about 20% of individuals with fractures have osteoporosis and at least 90% of all fractures are caused by a fall. Therefore, the present project builds on previous findings from our group identifying postural sway as an important risk factor for falls and aims to intervene against this risk factor in a randomized controlled trial targeting subjects at the highest risk for falls.

Specific aims:

1. Examine whether four weeks progressive balance training can improve parameters of body sway in measurements of static standing balance
2. Investigate whether participants experience greater security to their own ability and less fear of future falls after 4 weeks of progressive balance training
3. Investigate how long a potential effect of progressive balance training may be noticeable on participants' experiences of greater security in their own ability and less fear of future falls
4. 3. Examine whether participation in balance training leads to reduced number of falls at follow-up after 6, 12 and 24 months

Background

Falls and fall-related injuries are major health concerns for elderly individuals; they cause functional decline and increased mortality, as well as incurring vast health care costs for society.¹⁻³ Occurrences and consequences of falls are expected to increase globally with the growing number of elderly individuals. Hence, the improved detection and prediction of potential fall risk markers are of individual and societal importance.

Falling can be the end result of intrinsic and extrinsic factors negatively affecting an individual's ability to maintain balance,⁴ which are often revealed during sequences of body movement.⁵ Balance can be both dynamically and statically measured, the latter involves having the individual in a stationary standing position, from which results researchers have proposed impaired postural stability as a risk factor for falling.^{6,7} However, evidence regarding the association of postural instability with prospective falls is limited, and population-based cohort studies in this field are scarce.⁸ Other shortcomings of previous studies include the use of retrospective study designs,⁹ which increase the risks of recall bias and the identification of risk factors as the result of falls.^{10,11}

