Postural instability is preferably investigated using objective measures of posturography, the advantages of which over regular clinical assessments include the reduction of test performance variability and avoidance of subjective scoring systems.¹² Recently, researchers have analyzed the performance of the Wii Balance Board (WBB; Nintendo, Kyoto, Japan) in the measurement of postural instability; WBB-based assessment has shown excellent concurrent validity and the ability to complement existing fall assessments.^{13,14}

As of 2012, all 70-year olds in the Umeå municipality are invited to participate in the Healthy Ageing Initiative (HAI) study, which has currently enrolled more than 3000 participants.

Among other measurements, we include assessment of postural stability using a Wii Balance Board (WBB; Nintendo, Kyoto, Japan) device. With each participant in a quiet stance, balance trials consisting of 60-second eyes-open (EO) and eyes-closed (EC) trials are performed. Participants are instructed to maintain an upright position throughout the test, stand relaxed, and avoid any arm or head movement. The WBB measures total COP sway length, representing the sum of postural sway in the anteroposterior and mediolateral directions.

Preliminary results from our analysis of data consisting of 1900 70-year-old individuals revealed that participants with postural sway in the 5th quintile had almost twice the risk of

falling compared to the reference group, when the 1-year follow-up of prospective falls was performed.

Thus the aim of the present follow-up study is to investigate if we can reduce the increased postural sway of participants who have been identified as having abnormal balance values, based on previous measurements.

Project description

Study design

The present project is planned to be conducted as a 4-week randomized intervention study with a follow up time of 2 years.

Study population

Recruitment of individuals at high risk of falls from the Healthy Ageing Initiative

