The Healthy Ageing Initiative (HAI) is an ongoing population based project aiming to reduce risk factors for non-communicable diseases (NCD) by risk factor evaluation and increased physical activity.¹⁵ In short, HAI is inviting all 70 year olds in Umeå municipality to a health examination where traditional and potential novel risk factors for diabetes, CVD and fractures are investigated. These include objective measures of physical activity, blood pressure, blood-glucose, objective measured abdominal fat mass and ectopic fat, bone density and other features of bone quality, cognitive function, balance, walking ability, and different life style factors. At the second visit, all participants are informed about the results of tests performed and gets advice with a focus on physical activity, aiming at decreasing the risk of future diabetes, CVD and fractures. The counseling with focus on physical activity is based on motivational interviewing (MI) which is a directive patient-centered counseling style to help the participants to explore and resolve their ambivalence about behavior change. They are

contacted at 6 months and 12 months per telephone for follow up and are contacted for an in-clinic follow up after 5 years.

Participants in HAI identified as being in the highest quartile of measures of postural sway, indicating poor balance and high fall risk, are invited to participate by telephone contact, and will upon agreement be randomized into either the intervention group or control group.

Participants will after the initial contact also receive written information about the study. We aim to recruit 90 individuals from the existing HAI study cohort

Study protocol

Please see figure 1 for figure of study protocol.

Intervention protocol

Group 1

Twenty participants are randomised into the intervention group. The intervention group will perform group training sessions a week, consisting of 30 minutes of training for 4 weeks.

Group 2

Forty participants are randomised into the control group and receive a health consultation that highlights the importance of physical activity and balance exercise according to standard practice within the HAI project. They are asked to return after 4 weeks for follow up.

Follow up

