After 4 weeks, the groups are followed up with the same measures that are used in the Healthy Ageing Initiative that contains objective and functional balance tests, tests of muscle strength and a validated questionnaire on fear-of-falling and physical activity. Both groups will be offered the specific program for balance training post measurements, with instructions that it can be performed in the home setting according to the same principles offered to the intervention group. The groups are followed up after 6 and 12 months through 70-years-health checks on prospective falls and levels of physical activity.

Methods used for baseline and follow up

Measurements of postural stability

Postural stability is assessed using a Wii Balance Board (WBB) device (Nintendo, Kyoto, Japan) labeled “Nintendo RVL-WBC-01”, with a nominal sampling frequency of 100 Hz. The equipment is linked to a PC via Bluetooth connection “E1310E(00**”, using drivers labeled

intervention
three supervised
minutes of balance

“Manage Library for Nintendo’s Wiimote v1.7.00 by Brian Peek”. The software was designed in Microsoft C# by [name], Umeå University. The equipment’s power supply has been exchanged from battery to USB power. The validity and reliability of the WBB has been evaluated elsewhere, showing excellent conformation to other laboratory balance equipment, with mean differences in center of pressure (COP) variance ranging between 0.3 to 3%.¹³

Participants are examined during quiet stance involving trials of eyes open (EO) and eyes closed (EC) for 60 seconds each. Participants are instructed to maintain an upright position throughout the test and stand relaxed, while avoiding any arm or head movements. The WBB measures total COP sway length, representing the sum of postural sway in anteroposterior and

Measurements of physical activity and capacity

Participants will be asked to complete the short form of the International Physical Activity Questionnaire (IPAQ),¹⁷ an instrument designed to estimate activity levels among adult populations in domains including: 1) leisure time PA, 2) domestic and gardening activities, 3) work-related PA and 4) transport-related PA. Individuals are asked to recollect the duration of activities (walking, moderate- and vigorous- intensity PA) during the last 7 days in each domain. Questionnaire responses are used to calculate MET-min data in accordance with IPAQ guidelines.¹⁷

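### Follow up describes no 24-month contact and does not explicitly schedule FES-I or FES after week 4, and offering the programme to both groups limits what comparisons after week 4 can show

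*Combined protocol and SAP*

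**What the plan says.** Specific aims sets two questions that reach beyond the 4-week intervention. Aim 3 is to "Investigate how long a potential effect of progressive balance training may be noticeable" in participants' confidence and fear of falling. The fourth aim, printed with a double number, concerns "reduced number of falls at follow-up after 6, 12 and 24 months". Study design describes a "4-week randomized intervention study with a follow up time of 2 years".

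Follow up describes a week-4 visit using HAI's measures: balance tests, strength tests and a questionnaire on fear of falling and physical activity. After those measurements both groups are offered the balance programme, which can be done at home. The section then ends: "The groups are followed up after 6 and 12 months through 70-years-health checks on prospective falls and levels of physical activity".

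FES-I (16 items) and the original FES (13 items) are described under the heading Methods used for baseline and follow up, with no time points. The Statistical analysis plan names paired and independent t-tests for group differences and gives no time points either. Figure 1 is cited for the study protocol but is not shown in the text available for review.

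**The concern.** Three things do not fit together.

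- **24-month falls.** The time point is promised in two places, but the section that describes follow-up stops at 12 months.
- **Persistence of confidence and fear of falling.** Aim 3 needs repeated measurement after week 4. The sentence that gives the content of the later contacts names falls and physical activity and does not mention these outcomes.
- **Meaning of later comparisons.** Once controls have been offered the programme, the two arms no longer represent training and no training. Neither the aims nor the SAP says so.

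If staff followed the Follow up section as written, aim 3 would have a single post-baseline value per person. That value answers aim 2 but cannot show how long an effect lasts, and measurements missed at 6 or 12 months cannot be recovered. Even with complete later data, aims 3 and 4 could be misread if later differences were reported as the effect of training against none.

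**Working it through.** The plan gives no figure to reproduce, so the check sets what the aims need beside what the text describes.

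| Needed | Source of the need | Described in Follow up? |
|---|---|---|
| Fear of falling, week 4 | Aim 2 | Yes |
| Fear of falling and confidence after week 4 | Aim 3 | Not explicitly, at any time point |
| Falls, 6 months | Aim 4 | Yes |
| Falls, 12 months | Aim 4 | Yes |
| Falls, 24 months | Aim 4 and Study design | No |

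**Does the parent cohort fill the 24-month gap?** Study population says HAI participants are "contacted at 6 months and 12 months per telephone for follow up and are contacted for an in-clinic follow up after 5 years". None of these contacts falls at 24 months. The only HAI falls follow-up mentioned, in the background, is at one year: "when the 1-year follow-up of prospective falls was performed". So 24-month follow-up is plainly intended, but the visible text does not say how participants are contacted or how falls are recorded at that point.

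**Does the Methods heading schedule FES-I and FES?** The same heading covers the balance board, the Timed-Up-and-Go test, grip strength and IPAQ, and gives none of them a time point. It cannot mean every instrument at every contact if the 6- and 12-month contacts are HAI's telephone calls, because a balance-board test cannot be done by telephone. The heading therefore does not settle when FES-I and FES are given.

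**What do later between-group comparisons compare?** Following the sequence in Follow up:

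1. Up to week 4, the intervention group has supervised group sessions (the word supervised survives in a displaced fragment of the text) and the control group has the HAI health consultation.
2. Week-4 measurements are taken.
3. Both groups are offered the programme for home use.
4. The contacts at 6 months and later follow.

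Week 4 is thus the only comparison made before controls are offered the programme. From step 4 on, the contrast is initial group training plus the offered programme against consultation plus the offered programme. A difference that narrows could mean that the effect faded or that controls took up training. A difference that lasts could mean a durable effect or continued home training in the intervention group. Nothing in the aims or SAP separates these explanations.

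**The case against.** The strongest objection is Figure 1. It is cited just before the intervention and follow-up text, where a contact schedule could well sit, and its absence from the extracted text is not a fault in the plan. This stands, so the 24-month and aim 3 parts are conditional on it. If the figure does hold the schedule, Follow up still has to agree with it.

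The second objection concerns the questionnaires. The plan treats the fear-of-falling questionnaire as one of HAI's measures, refers to a single questionnaire covering both fear of falling and physical activity, and runs the 6- and 12-month follow-up through the 70-year health checks, with physical activity named there. The sentence on those contacts does not say that nothing else is collected. This also stands, so later collection of FES-I or FES is a plausible reading. A reader might infer that fear of falling is not measured after week 4, or that no 24-month data will exist. The documents do not support either inference. They support only that these items are not explicitly described.

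A third objection is that the offer to both groups is openly stated. It is, and the offer is not criticised here. What is missing is its consequence for interpretation. A reader might call the later contrast early against delayed training. That does not fit the text, because the intervention group is offered the programme again and the later version can be done at home, unlike the initial group sessions.

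**Conclusion.** The point holds in a limited form and should be fixed. On the visible text, one of the three falls time points (24 months) has no described contact, and aim 3 has one post-baseline time point at which its outcome is explicitly scheduled. Both statements assume that Figure 1 does not supply the schedule. The limit on interpreting comparisons after week 4 does not depend on Figure 1, because it follows from the offer described in Follow up.

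The 4-week sway question and aim 2 are unaffected. No bias or loss of precision can be quantified: the documents give no expected uptake of the programme in controls and no expected continuation in the intervention group.

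**What to change.** 1. **Aim 3.** State in Follow up that FES-I and FES are collected at the existing 6- and 12-month contacts, or drop the aim. Keeping it adds 16 + 13 = 29 items per person per contact, possibly by telephone since HAI's contacts at those times are calls. Dropping it costs one stated aim.
2. **24 months.** Reconcile aim 4, Study design and Follow up: either add a 24-month falls contact to Follow up, or limit the aim and the stated duration to 12 months. The first costs one extra contact per participant if none is planned; the second is wording only.
3. **Interpretation.** State in the aims and SAP that week 4 is the only comparison made before controls are offered the programme. State also that later comparisons are of initial supervised group training plus the offered programme against HAI consultation plus the offered programme, and limit conclusions to that contrast. This is wording only.

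If Figure 1 already shows the schedule, copying it into Follow up settles items 1 and 2 at no further cost. Item 3 is needed either way.

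### Falls are an aim at 6, 12 and 24 months, but the plan describes only 6- and 12-month contacts and no running record, so counts would rest on about six months' memory

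*Combined protocol and SAP*

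**What the plan says.** The last aim under Specific aims asks whether balance training leads to a "reduced number of falls at follow-up after 6, 12 and 24 months". Study design describes a "4-week randomized intervention study with a follow up time of 2 years".

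The Follow up section is the only place that says how falls will be obtained: the groups are "followed up after 6 and 12 months through 70-years-health checks on prospective falls". The account of the Healthy Ageing Initiative (HAI) under Study population says that its participants are "contacted at 6 months and 12 months per telephone for follow up", with the next clinic contact at 5 years. No 24-month contact is described.

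The section on methods for baseline and follow-up covers sway, the physical activity questionnaire, Timed Up and Go, grip strength, the two falls-efficacy questionnaires and anthropometry. It has no entry for falls. It gives no definition of a fall, recording tool, recall window or question wording, and does not say whether the person asking is blind to arm.

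On earlier research, the Background says "Other shortcomings of previous studies include the use of retrospective study designs", "which increase the risks of recall bias and the identification of risk factors as the result of falls".

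**The concern.** A fall that causes no injury is easily forgotten. If nothing is written down when it happens, and the next described question comes at 6 months and then at 12, the count is whatever the participant can recall over about half a year. The authors name recall bias as a weakness of earlier studies, but describe no safeguard against it here.

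Two separate things are at stake for the falls aim. Forgetting that is equal in both arms removes events from a small trial. Forgetting or reporting that differs between arms biases the comparison itself. The second is possible because participants know whether they attended group training or only "receive a health consultation that highlights the importance of physical activity and balance exercise". The trial also sets out to learn whether training changes how safe people feel; the second aim begins "Investigate whether participants experience greater security to their own ability and less fear of future falls after 4 weeks". A change in confidence could alter how readily a minor stumble is remembered or mentioned, in either direction.

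**Working it through.** **1. The passages side by side**

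| Place | Falls time points |
|---|---|
| Specific aims | 6, 12 and 24 months |
| Study design | 2 years of follow-up |
| Follow up | 6 and 12 months |
| Study population (HAI contacts) | 6 and 12 months by telephone, then clinic at 5 years |

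The described contacts leave recall intervals of 0–6 and 6–12 months. A 24-month contact, if added with nothing in between, would have a 12-month interval. The documents contain no fall rate, recall figure or sample-size calculation, so there is no plan figure to reproduce. Everything below is illustration on stated assumptions.

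**2. Equal recall in both arms**

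Assume that 75–90% of falls are recalled. Share lost = 1 − recall: 1 − 0.90 = 10% and 1 − 0.75 = 25%. The ratio between arms is unchanged.

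To put this in events, take the arm sizes given under Intervention protocol, 20 trained and 40 control, and assume 0.3–0.7 falls per person-year. (These arms sum to 60, not the recruitment target of 90, which is a separate matter.)

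- Trained: 20 × 0.3 = 6 to 20 × 0.7 = 14 falls in a year.
- Control: 40 × 0.3 = 12 to 40 × 0.7 = 28 falls in a year.
- Lost from the trained arm: 0.10 × 6 = 0.6 to 0.25 × 14 = 3.5.

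**3. Unequal recall**

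Observed ratio = true ratio × (recall in trained ÷ recall in control). With a true ratio of 1.00:

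| Recall, trained | Recall, control | Observed ratio |
|---|---|---|
| 0.75 | 0.90 | 0.75/0.90 = 0.83 |
| 0.80 | 0.90 | 0.80/0.90 = 0.89 |
| 0.90 | 0.75 | 0.90/0.75 = 1.20 |

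The extremes, 0.83 and 1.20, put the arms at opposite ends of the assumed range. They bound the illustration and are not a forecast.

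**4. How this compares with chance error**

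If falls were Poisson, the 95% interval for the rate ratio would extend by a factor of exp(1.96 × √(1/a + 1/b)) either way, where a and b are the falls in each arm.

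- a = 6, b = 12: √(1/6 + 1/12) = 0.50, factor exp(0.98) = 2.7.
- a = 14, b = 28: √(1/14 + 1/28) = 0.327, factor exp(0.641) = 1.9.

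Repeat fallers would widen this further. A shift to 0.83 or 1.20 lies well inside it.

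**5. Power**

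Assume 15–35% of controls fall at least once in 12 months, a true risk ratio of 0.5, arms of 40 and 20, and a two-sided 5% level. Power by normal approximation is Φ((d − 1.96·SE₀)/SE₁), where d is the difference in proportions, SE₀ its pooled and SE₁ its unpooled standard error. At 25% versus 12.5%: d = 0.125, SE₀ = 0.111, SE₁ = 0.101, power 18%.

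| Reporting, equal in both arms | Power across 15–35% |
|---|---|
| 100% | 10% to 27% |
| 85% | 9% to 22% |
| 70% | 8% to 17% |

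The falls comparison is weak even with perfect recording, and under-reporting weakens it further.

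**The case against.** The strongest reply is that the documents never say falls are collected by recall. They do not state the method. Collection sits within HAI, which has already run a one-year prospective falls follow-up whose procedures are not described here, and the study figure is not available in the text reviewed. This stands: a reader might infer that recall is the only source, but that is an inference from silence. What can be said is that no other method is described. If a tool exists, the protocol still needs to name it.

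A reader might also infer that the trial mislabels its falls as prospective and repeats the fault it criticises. The documents do not support that. Falls here occur after the sway measurement and after randomisation, so the word is correct in the design sense, and the Background's worry that risk factors may result from falls does not apply. Only the recall half of that criticism carries over.

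Third, both groups are offered the programme after the 4-week measurement, before either falls contact, and the persistence of any gain in confidence is itself an open question in the third aim. This weakens the idea that feeling safer would separate the arms at 6 or 12 months. It does not remove it, because participants still know their original allocation.

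Fourth, falls are the last aim in a trial built around sway, and the possible bias is small beside chance error (steps 4 and 5). That limits the importance of the point. It is not a reason to leave the method unstated, since more participants would narrow the interval but would not correct a bias between arms.

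Finally, participants who know their arm would fill in a calendar themselves, could back-fill it between week 4 and month 6, and might keep it better in the arm with supervised sessions. All of this stands and shapes the fix.

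**Conclusion.** The point holds in a limited form. As described, falls counts would depend on memory over about six months, with no stated definition or running record, and one of the three time points in the aim has no described contact. Falls may be under-counted, by 10–25% if recall is 75–90%. Reporting may also differ by arm; on the same assumption a true rate ratio of 1.00 could appear as anything from 0.83 to 1.20.

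A reader might go further and conclude that falls will certainly be missed, or that the trained arm will under-report and so show a false benefit or hide harm. The documents support neither. They contain no recall figure, the direction of any difference is unknown, and they describe no use of falls to judge harm. The recall range and fall rates are assumptions throughout. The sway result is untouched. This is a cheap improvement to a secondary part of the trial, best made before follow-up begins, because a fall not recorded at the time may not be recoverable later.

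**What to change.** - State a one-line definition of a fall.
- Give every participant in both arms the same dated falls calendar at entry. Check it at the week-4 visit and read it out at the 6- and 12-month contacts.
- Either continue the calendar to a 24-month contact or remove 24 months from the aim, so that Specific aims, Study design and Follow up agree.
- Use calendar counts for the falls analysis and recall only where no calendar was kept. Report the source of counts by arm, and repeat the comparison in calendar-keepers only as a sensitivity analysis. This shows whether calendar-keeping differs between arms, but it does not correct for it.
- If HAI already uses a running record, name and describe it instead.

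The cost is one printed sheet per participant, read at contacts already planned, with no new visit unless the 24-month time point is kept. The downside is a small burden on participants and some incomplete calendars. The calendar reduces forgetting; bias from unblinded self-report remains and should be acknowledged when the falls results are reported.

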Participants will also be asked to perform the Time-Up-and-Go (TUG) test,¹⁸ commonly used by clinicians to assess lower leg muscle strength, gait performance and overall functional mobility in elderly individuals. Testing involves participants rising unaided from an armchair and walking forward 3 meters until they reach a selected line on the floor, at which point they turn and come back to a seated position. Research nurses provides instructions and measures total testing time using a stopwatch. The TUG test have previously demonstrated good inter-

rater reliability (ICC=0.99).¹⁸ Testing of isometric muscle strength involves using a hydraulic hand dynamometer (Jamar, Patterson Medical, Warrenville, IL, USA) to measure participant's maximum grip strength in the non-dominant hand. Participants will be instructed to keep the arm angled at 90° and maintain the elbow in proximity to the waist during the test. The maximum value out of 2 consecutive attempts is subsequently recorded.

Measurement of Confidence in Balance Ability and Fear-of-Falling

Participants will also be asked to report confidence in balance ability and fear of falling. This will be accomplished through two questionnaires. The Falls Efficacy Scale International (FES-I) measures fear of falling and is comprised of 16 questions on a scale from 1-4.¹⁹ The Original Falls Efficacy Scale (FES) is also included and measures confidence in balance ability, formed by answering 13 questions on a scale from 1-10.²⁰

Anthropometric measures

Anthropometric data will be obtained using a scale (HL 120; Avery Berkel, Fairmont, MN, USA) to measure weight, and a gauge (Holtain Limited; Crymych, Dyfed, UK) to measure height.

Statistical analysis plan

Descriptive data will be presented as means + standard deviations and the Student's t-test will be used to analyze statistical differences between variables. Categorical variables are investigated using chi-squared tests. Potential differences between intervention and control group will be analyzed using paired and independent t-tests. All analyses will be performed with SPSS version 24 (IBM Corp, Armonk, NY, USA) and Stata version 13.1 (StataCorp, College Station, Texas, USA).

Ethical considerations

Importance

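### The SAP assigns both paired and independent t-tests to the intervention–control comparison without saying which decides or on which variable, and does not adjust for the baseline sway it collects

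*Combined protocol and SAP*

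**What the plan says.** The section Statistical analysis plan is one short paragraph. On the comparison of arms it has one sentence: "Potential differences between intervention and control group will be analyzed using paired and independent t-tests". Besides that it names a Student's t-test in general terms and chi-squared tests for categorical variables. No regression model or covariate appears anywhere in the document.

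Sway is available before and after training. It is measured in the Healthy Ageing Initiative (HAI), and "After 4 weeks, the groups are followed up with the same measures that are used in the Healthy Ageing Initiative". It is recorded with eyes open and with eyes closed, 60 seconds each; neither condition is called primary, and aim 1 speaks of sway parameters in the plural.

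Entry depends on sway. Those invited are "Participants in HAI identified as being in the highest quartile of measures of postural sway, indicating poor balance and high fall risk", and the Background gives the aim as to "reduce the increased postural sway of participants who have been identified as having abnormal balance values, based on previous measurements".

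The text does not say whether that qualifying reading is the trial baseline or a new one is taken. Two phrases hint at an opening visit: the tests are headed "Methods used for baseline and follow up", and of the controls it is said that "They are asked to return after 4 weeks for follow up". Study protocol adds "Please see figure 1 for figure of study protocol"; that figure is not shown in the text available for this review and may settle the matter.

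On size, Intervention protocol gives twenty and forty participants, while Study population says "We aim to recruit 90 individuals from the existing HAI study cohort".

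**The concern.** A paired t-test compares before with after in the same people. It cannot estimate a difference between two randomised arms, yet the sentence attaches it to that difference. The independent t-test can, but the sentence permits two versions of it, on week-4 sway or on change. They differ in power, and which is stronger depends on a correlation nobody has stated. Three things are at stake:

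- **Precision.** In a small trial, ignoring a baseline value already in hand can waste power.
- **An open choice.** If the version reported can be chosen after the data are seen, the 5% error rate is not kept.
- **A conditional misreading.** If the baseline is the reading that qualified people for entry, mean sway will fall in both arms without any training effect, and a within-arm paired test could be presented as evidence of benefit.

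**Working it through.** The plan states no power, significance level, SD, effect size or correlation, so it has no figure to reproduce. What follows is an illustration.

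**From the documents:** arms of 20 and 40 (Intervention protocol); selection from the top quartile of sway (Study population); outcome at 4 weeks (Follow up).

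**Assumed:** normally distributed sway in population SD units; selection on one reading; any two readings correlated r, with r = 0.3 to 0.9; no repeat-test effect; two-sided 5% tests; true effect 0.5 population SD.

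**Step 1, selected group.** Top quartile of a standard normal: mean = φ(0.674)/0.25 = 1.271; variance v = 1 + 0.674 × 1.271 − 1.271² = 0.242.

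**Step 2, variance that each analysis works with.**
- Week-4 value, either baseline: V = r²v + 1 − r²
- Fresh baseline: change 2(1 − r); adjusted V − c²/V, where c = r²v + r − r²
- Qualifying reading as baseline: change (1 − r)²v + 1 − r²; adjusted 1 − r²

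At r = 0.7: V = 0.49 × 0.242 + 0.51 = 0.628.
- Fresh baseline: change 0.600; c = 0.118 + 0.21 = 0.328; adjusted 0.628 − 0.328²/0.628 = 0.457. Adjustment removes 1 − 0.457/0.628 = 27% of the week-4 variance and 1 − 0.457/0.600 = 24% of the change variance.
- Qualifying reading: change 0.09 × 0.242 + 0.51 = 0.532; adjusted 0.510. The reductions are 19% and 4%.

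**Step 3, power at 20/40.** The standard error is √(variance × (1/20 + 1/40)). For the week-4 test at r = 0.7 it is √(0.628 × 0.075) = 0.217, and 0.5/0.217 = 2.30, which gives about 62% power. Simulated power, as week-4 / change / adjusted:

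| r | Fresh baseline | Qualifying reading as baseline |
|---|---|---|
| 0.3 | 46 / 33 / 48% | 45 / 42 / 45% |
| 0.5 | 52 / 44 / 58% | 52 / 52 / 54% |
| 0.7 | 62 / 64 / 75% | 62 / 69 / 70% |
| 0.9 | 82 / 98 / 99% | 83 / 98 / 98% |

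The better of the two t-tests changes with r. Against that better test, adjustment gains 2, 6, 11 and 1 points with a fresh baseline, and 0, 2, 1 and 0 points with the qualifying reading.

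**Step 4, choosing after seeing the data, zero effect.** Each single between-arm test, adjusted or not, rejects in about 5% of trials. Counting a trial as positive if either the week-4 or the change t-test is significant gives about 7 to 10%. The lower end belongs to the qualifying reading as baseline, the upper end to a fresh one.

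**Step 5, paired tests, zero effect, qualifying reading as baseline.** The expected fall in sway is (1 − r) × 1.271.

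| r | Expected fall (SD) | Training arm (20) improves | Controls (40) improve | Training only |
|---|---|---|---|---|
| 0.3 | 0.89 | 96% | 100% | 0% |
| 0.5 | 0.64 | 85% | 99% | 0.7% |
| 0.7 | 0.38 | 60% | 90% | 6% |
| 0.9 | 0.13 | 23% | 43% | 13% |

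With a fresh baseline the last column is about 2.5% at every r.

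**The case against.** The ordinary meaning of such a sentence is paired tests within arms and independent tests between them. On that reading a valid between-arm test is already planned, and a change-score t-test, which the wording allows, already uses the baseline. This largely stands: no error in the planned estimate has been shown. But even the charitable reading leaves week-4 versus change undecided and does not stop a claim resting on a within-arm result.

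The gain from adjustment is not assured either. HAI has been running since 2012, so a qualifying reading could be years old and r low. If that reading is the baseline, the table shows gains of 0 to 2 points over the better t-test. That stands; the material gain needs a fresh baseline and a middling r.

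A reader might infer that regression to the mean will probably produce a false claim of benefit. The documents do not support that. It requires that no new baseline is taken, which is the less supported reading given the hints of an opening visit. Even then, at low r the controls improve almost always too, so there is no contrast to misreport. The most striking figure, 96% of training arms improving, comes with 100% of control arms doing so. Nor should one work from equal arms, where the training-only result would be more frequent: no section states that allocation.

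**Conclusion.** The point holds as a matter of specification and precision. The deciding test, its variable and the sway condition are not fixed, and collected baseline information is not used. It would be wrong to infer that the randomised comparison is biased or invalid: the independent t-test keeps its 5% error rate with either baseline.

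The cost that does not depend on which reading is baseline is the open choice of test, about 7 to 10% error instead of 5% if it is exploited. The precision cost relative to the better t-test is about 1 to 11 points of power with a fresh baseline and about 0 to 2 points with the qualifying reading. Relative to the worse t-test it can be larger: with a fresh baseline, 15 points at r = 0.3 (48 against 33) and 17 at r = 0.9 (99 against 82). The risk from paired tests is conditional, about 0 to 13% of trials at 20/40 against about 2.5% with a fresh baseline.

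All figures rest on the assumed normality, r and effect size, and on 20/40; the documents do not reconcile 20 + 40 = 60 with the 90 to be recruited. They concern sway only; none is claimed for the Falls Efficacy Scales or the Timed Up and Go test. The change should be made before the data are analysed.

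**What to change.** Replace the sentence in Statistical analysis plan with:

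> The effect of training is the between-group difference in 4-week COP sway length, in one pre-named condition (eyes open or eyes closed), from a linear regression on group and baseline sway in that condition, with 95% CI; the other condition is secondary. The same model, with the outcome's own baseline value, is used for FES-I, FES and TUG where a baseline value is collected. Within-group paired comparisons are descriptive only and are not used to claim an effect.

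Fill in the chosen condition before any outcome data are seen, and state in the text which sway reading is the baseline.

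The cost is SAP wording and one degree of freedom. SPSS and Stata, both already named, fit the model. No extra participants or visits are needed, because either reading can serve as the covariate.
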